## 12.8 \* Secondary Outcome(s)

Indicate which **additional variable(s)** will be assessed to judge the secondary outcome(s). Give measurement units, if applicable.

- a. Gene expression profiles in the mucosa and submucosa compartments in humans before and after course of antibiotics.
- b. Gut microbiota changes in humans after course of antibiotics.
- c. Gut metabolites changes in humans after course of antibiotics.

## 12.9 \* Methods and Procedures

Please provide a description of the laboratory and clinical analyses and procedures that will be performed. Include the role of external collaborators and consultants when appropriate. Please refer to Help text for Guidance.

One set of samples will be studied: Colorectal sample tissue and stool from amoxicillin-treated participants. All samples will be collected from RUH volunteers.

Ten 18–75-year-old participants will be divided into two groups of 5 and matched in age +/- 5 years, race, sex, and gender.

There will be five (5) study visits:

### Study Visit 1 (Screening Visit) (approximately 2 hours; Out-Patient Visit)

- Consent process
- Medical History
- Targeted physical exam (focus on GI, cardiac and respiratory)
- HIV test
- POC Pregnancy test for women of childbearing age
- Labs: venipuncture to collect CBC, Comprehensive metabolic panel, PT/PTT, INR for a total of 10 ml blood (2 tps.).
- Instructions will be provided in preparation for Visit #2. The following will be included:

- a. adhere to a clear liquid diet the day prior to the scheduled flexible sigmoidoscopy. A clear liquid diet sheet with examples will be given to each participant.
- b. The evening prior to the flexible sigmoidoscopy, participants will cleanse their bowels with a tap water enema. A plastic bottle and K-y jelly will be given to the participants to take home.
- c. a sealed commercial stool collection kit (DNA Genotek) that includes specimen collection instructions, toilet accessory, collection tubes, and spatulas will be given to the participants to collect stool prior to the procedure. The participant will bring the stool sample during visit #2, +/- 2 days.
- c. NPO after midnight the day of the procedure but encourage sips of water.

Further instructions will be given to participants on how to avoid prebiotics and probiotics during the study and to notify the PI if they need to take any antimicrobials or any new medications, start a new diet, have enteric infections during the study as these may result in their exclusion from the study.

Upon review of lab results and if the participant meets eligibility criteria, the PI will contact the study participant to schedule the flexible sigmoidoscopy. The participant will be instructed to adhere to a clear liquid diet the day before the procedure, to self-administer the tap water enema in the evening prior to the procedure, and not to eat or drink anything (except sips of water) after midnight the day of the procedure.

**VISIT #2: Procedure Visit ( 2 to 21 days after screening visit) (approximately 2 hours; Day Patient Visit)**

- Stool sample will be collected and stored in the refrigerator.
- Vital signs pre- and post-procedure. Post-procedure, vital signs will be taken immediately after the procedure, then 30 minutes after the procedure, and 1hr after the procedure.
- POC Urine Pregnancy test for women of childbearing age.
- Stool consistency and frequency questionnaire will be given to the participant to complete.
- Oral diazepam 5 mg pre-procedure will be offered and administered based on the patient preference and PI evaluation. Oral diazepam takes 30 - 60 minutes to take effect.
- Tap water enema upon arrival followed by additional 1 or 2, 200ml tap water enemas if the participant still has solid debris after a bowel movement.
- Flexible Sigmoidoscopy Procedure
  - The sigmoidoscope is advanced to the beginning of the descending colon (about 24 cm) and up to 20 biopsies will be obtained with Boston Scientific Jumbo forceps (max diameter of 2.8mm), each biopsy will be 2-2.8 mm in size, one in each quadrant, spaced 2-3cm throughout the sigmoid colon.
  - Tissue specimens will be placed in sterile specimen cups containing normal saline.
- Observation for one-hour post-procedure (for signs of bleeding or distress) and evaluation by nursing and PI to determine when ready for discharge.
- Breakfast
- Post-procedure Instruction sheet given prior to departure.

In the event a mass, polyp, or ulceration is found, a copy of the images obtained during the sigmoidoscopy and a letter with the examination findings will be given to the participant and they will be instructed to follow-up with their Primary Healthcare Provider.

The participant will be asked to return in two weeks for Visit #3 and instructions on avoiding the addition of new probiotics, prebiotics or drastic dietary changes will be given. In addition, participants will be instructed to notify us if he/she starts any antimicrobial medication including antifungals, or developed any intestinal infection.

**VISIT #3: Medication Visit (14 to 21 days after visit 2) (approximately 1 hour; Outpatient Patient Visit)**

- Medical History
- Targeted physical exam (focus on GI, cardiac and respiratory)
- POC Urine Pregnancy test for women of childbearing age
- Participants will be randomized to receive a 7-day supply of amoxicillin 875mg capsules to be taken every 12 hours. Medication will be dispensed and provided during the visit.
- Participants will be given a diary to record medication intake times.
- Participants will be given a plastic bottle and K-y jelly to self-apply a tap water enema at home on the night prior to the procedure.
- A sealed commercial stool collection kit (DNA Genotek) that includes specimen collection instructions, toilet accessory, collection tubes, and spatulas will be given to the participants to collect stool prior to the next procedure. The participant will bring the stool sample during Visit #4, +/- 2 days.

- Same instructions provided in preparation for Visit #2 will be provided in preparation for Visit #4.
- Same as in Visit #2 participants will be asked to avoid any new prebiotics, probiotics, or drastic dietary changes and to notify investigators if new anti-microbial medications were started or they developed an intestinal infection.

**VISIT #4: Procedure Visit (5-9 days after initiation of antibiotics) (approximately 2 hours; Day Patient Visit)**

Same as Visit #2. This visit could also occur after 5 Days of antibiotics in volunteers who cannot tolerate a 7-day course of amoxicillin. Participants that cannot tolerate at least 5 days of antibiotics will be excluded from the study, replaced with other participants, and provided partial compensation.

- Medication diary will be collected.
- Stool sample will be collected and stored in the refrigerator.
- Vital signs pre- and post-procedure. Post-procedure, vital signs will be taken immediately after the procedure, then 30 minutes after the procedure, and 1hr after the procedure.
- POC Urine Pregnancy test for women of childbearing age.
- Stool consistency and frequency questionnaire will be given to the participant to complete.
- Oral diazepam 5 mg pre-procedure will be offered and administered based on the participant's preference and PI evaluation. Oral diazepam takes 30 - 60 minutes to take effect.
- Tap water enema upon arrival followed by additional 1 or 2, 200ml tap water enemas if the participant still has solid debris after a bowel movement.
- Flexible Sigmoidoscopy Procedure
- The sigmoidoscope is advanced to the beginning of the descending colon (about 24 cm) and up to 20 biopsies will be obtained with Boston Scientific Jumbo forceps (max diameter of 2.8mm), each biopsy will be 2-2.8 mm in size, one in each quadrant, spaced 2-3cm throughout the sigmoid colon.
- Tissue specimens will be placed in sterile specimen cups containing normal saline.
- Observation for one-hour post-procedure (for signs of bleeding or distress) and evaluation by nursing and PI to determine when ready for discharge.
- Breakfast
- Post-procedure Instruction sheet given prior to departure.
- In the event a mass, polyp, or ulceration is found, a copy of the images obtained during the sigmoidoscopy and a letter with the examination findings will be given to the participant and they will be instructed to follow-up with their Primary Healthcare Provider.
- The participant will receive a sealed commercial stool collection kit (DNA Genotek) that includes specimen collection instructions, toilet accessory, collection tubes, and spatulas to collect stool prior to the next procedure. The participant will bring the stool sample during visit #5, +/- 2 days. similar to Visits #1 and # 3 to collect stool prior to Visit #5.
- Same as in Visit #3 participants will be asked to avoid any new prebiotics, probiotics, or drastic dietary changes and to notify investigators if new anti-microbial medications were started or they developed an intestinal infection.
- Participants will be given a plastic bottle and K-y jelly to self-apply a tap water enema at home on the night prior to the procedure.

**VISIT #5: Procedure Visit (21 to 30 days after Visit #4) (approximately 2 hours; Day Patient Visit)**

- Stool sample will be collected and stored in the refrigerator.

- Vital signs pre- and post-procedure. Post-procedure, vital signs will be taken immediately after the procedure, then 30 minutes after the procedure, and 1hr after the procedure.
- POC Urine Pregnancy test for women of childbearing age.
- Stool consistency and frequency questionnaire will be given to the participant to complete.
- Oral diazepam 5 mg pre-procedure will be offered and administered based on the patient preference and PI evaluation. Oral diazepam takes 30 - 60 minutes to take effect.
- Tap water enema upon arrival followed by additional 1 or 2, 200ml tap water enemas if the participant still has solid debris after a bowel movement.
- Flexible Sigmoidoscopy Procedure
- The sigmoidoscope is advanced to the beginning of the descending colon (about 24 cm) and up to 20 biopsies will be obtained with Boston Scientific Jumbo forceps (max diameter of 2.8mm), each biopsy will be 2-2.8 mm in size, one in each quadrant, spaced 2-3cm throughout the sigmoid colon.
- Tissue specimens will be placed in sterile specimen cups containing normal saline.
- Observation for one-hour post-procedure (for signs of bleeding or distress) and evaluation by nursing and PI to determine when ready for discharge.
- Breakfast
- Post-procedure Instruction sheet given prior to departure.
- In the event a mass, polyp, or ulceration is found, a copy of the images obtained during the sigmoidoscopy and a letter with the examination findings will be given to the participant and they will be instructed to follow-up with their Primary Healthcare Provider.

#### Lab Procedures

Sample processing and analysis.

A total of 20 biopsies will be obtained per participant: 4 will be used for tissue immunostaining and remaining 16 will be used for single nuclei sequencing. Tissue obtained from each region will be separated: four biopsies will be pinned and fixed in 4% paraformaldehyde overnight, followed by washing, permeabilization, and staining of the tissue with the neuronal antibody ANNA-1 and anti-Sox10 which is a glia antibody. We will image the samples with a confocal microscope, and we will count the neurons and glia. Sixteen biopsies will be snap frozen in liquid nitrogen and stored in a -80C freezer. Once several samples have been collected, we will defrost them and further process them into single nuclei suspensions that will be utilized to generate sequencing libraries with the 10X Chromium platform. We will sequence the nuclear RNA to determine the expression of multiple genes in the human intestine. Of note, we do not know what the nuclei yield will be for the pooled 16 biopsies obtained per participant, our target nuclei count will be about 20,000 in total. We will enrich the desired populations by staining the nuclei with anti-NeuN and anti-Sox10 to sort the neurons and glia populations respectively. We do not know what will be the proportions of the different cell types for this particular protocol, however, based on other studies we expect small proportion of glia and neurons thus making it necessary to pool samples from several participants. We will not sequence the human DNA. We will isolate bacterial DNA from the stool and perform 16S ribosomal RNA sequencing for which we have an optimized protocol in our lab. Moreover, we will identify and measure stool metabolites via Liquid Chromatography- Mass Spectrometry at RU Proteomics Core.

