#### 12.7 \* Primary Outcome(s)

Indicate which **variable(s)** will be assessed to judge the primary specific aim. Give measurement units, if applicable.

Total number of colonic submucosal neurons and glia cells in humans before and after course of antibiotics.

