**12.10 \* Data Analysis**

Describe method(s) of data analysis.

In this pilot study, with 10 participants, we will assess the change in the outcomes between baseline and follow up using a paired sample t-test. While exploratory, we will be able to detect a 1.3 standard deviation change in outcomes pre versus post, with greater than 80% power, holding Type I Error to 5%.

**12.11 \* Explain the rationale for the choice of statistical measures and the number of participants proposed for the study, including the power calculations when applicable.**

Assuming we can enroll 10 patients, we will have over 80% power to detect a 1.3 standard deviation difference in continuous outcome measures and a 38% absolute difference in proportions (assume base rate of 50%). This pilot study will also provide observed effect size for use in the design of future analysis.

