## 26.0 Compensation/Costs

### 26.1 \*Will any compensation be offered to participants in return for their participation, e.g., direct payment, medical care, tests, etc.?

- ☐ No  
☒ Yes (Please describe)

Please Describe

Participants will receive \$1100 for their participation and completion of the study.

- \$300 for each completed sigmoidoscopy procedure
- \$100 for completing a 7-day course of antibiotics

Participants will receive an additional \$100 for completion of all study visit requirements. If a participant only completes a portion of the study, they will receive partial compensation.

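### The laboratory plan counts 20 biopsies per participant where the visits allow up to 60, and the primary cell count has no tissue denominator

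*Combined protocol and SAP*

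**What the plan says.** Section 12.9 schedules a flexible sigmoidoscopy at Visits 2, 4 and 5. The biopsy text is the same at all three: "up to 20 biopsies will be obtained with Boston Scientific Jumbo forceps", each biopsy 2 to 2.8 mm, placed "one in each quadrant, spaced 2-3cm throughout the sigmoid colon". No minimum number is given.

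The Lab Procedures part of the same section gives the figure differently: "A total of 20 biopsies will be obtained per participant", of which "4 will be used for tissue immunostaining and remaining 16 will be used for single nuclei sequencing". It uses the same unit again further on: "we do not know what the nuclei yield will be for the pooled 16 biopsies obtained per participant". The neurons and glia are counted by confocal microscopy on the stained biopsies.

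Section 12.7 defines the primary outcome as "Total number of colonic submucosal neurons and glia cells in humans before and after course of antibiotics". No unit of area, biopsy or ganglion is attached. Section 12.10 supplies none either; it says that "we will assess the change in the outcomes between baseline and follow up using a paired sample t-test".

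Section 21.1 names perforation, infection and bleeding as risks of the procedure but does not say how many biopsies a participant undergoes.

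**The concern.** There are two linked problems.

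First, the number of biopsies per participant is 20 in one place and up to 60 in another. A reader who wants the tissue available at each time point, or the total exposure of one participant, cannot settle it from the application text, and the risk section does not help.

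Second, the stained biopsies produce the primary outcome, and that outcome is a raw total. A raw total rises and falls with the amount of tissue imaged. If two visits of one participant differ in the number or size of the biopsies imaged, the paired difference moves although nothing has changed in the gut. The study hypothesis predicts a loss of neurons, so less tissue after treatment would look like the expected effect. With 10 participants there is little room for such shifts to average out.

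**Working it through.** **1. The laboratory figure itself.** 4 stained + 16 sequenced = 20. The split adds up; the question is the unit to which it belongs.

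**2. Number of procedures.** Section 12.9 has three procedure visits (2, 4 and 5). Section 26.1 agrees: $300 "for each completed sigmoidoscopy procedure", $100 for the antibiotic course and $100 for completing all visits. 3 × 300 + 100 + 100 = $1100, the stated total.

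**3. Biopsies per participant.**

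| | 20 is per procedure | 20 is per participant |
|---|---|---|
| All biopsies, per participant | up to 3 × 20 = 60 | 20 |
| Stained | 3 × 4 = 12 | 4 |
| Sequenced | 3 × 16 = 48 | 16 |
| All biopsies, 10 participants | up to 600 | 200 |

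The largest possible gap is 60 / 20 = 3. The visit figure is a ceiling, so the real gap may be smaller.

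**4. Which unit is more plausible.** Four quadrants at five levels give 4 × 5 = 20 in a single procedure (five levels is an assumption; the text gives only the quadrants and the spacing). Four stained biopsies cannot be shared evenly over three visits. The visit text is consistent across all three procedures. All of this favours a figure per procedure.

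**5. How far the raw total can move with tissue alone, on the per-procedure reading.**

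- Size: if 2 to 2.8 mm is a diameter, area is π(d/2)². At 2 mm this is 3.14 mm² and at 2.8 mm it is 6.16 mm². The ratio is (2.8/2)² = 1.96. For four stained biopsies the range is 12.6 to 24.6 mm². The full 1.96 is an extreme, with every biopsy at the lower limit at one visit and at the upper limit at the other.
- Number: as an illustration, if four biopsies are imaged at one visit and three at the next, with equal cell density and size, the total changes by (3 − 4)/4 = −25% with no change in biology.

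**6. Stated power.** Sections 12.10 and 12.11 give more than 80% power for a change of 1.3 SD with 10 participants. A paired t-test with n = 10 and two-sided 5% has noncentrality 1.3 × √10 = 4.11 on 9 degrees of freedom, and its power is 95.4%. The claim of more than 80% is true, and biopsy number does not enter it.

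**The case against.** The strongest reply is that this is a slip of wording. The visit procedures determine what is taken from a participant, and they agree with each other: at most 20 each time. The laboratory paragraph describes how tissue is processed. It also lists the four stained biopsies first and calls the sequencing biopsies the remainder, which suggests that staining is filled first. The Schedule of Events is a separate attachment and the consent pages are not available, so the number may be clear there. Enrollment closed on May 24, 2024, and section 14.1 projects no outpatient or Day Patient visits for the next year, so rules on collection may come too late.

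Most of this stands. It makes the conflict one of wording and limits what can still be changed. It does not supply a denominator for the primary outcome or a minimum number of biopsies, and an implied order of filling is not a stated rule.

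Three stronger readings are tempting, and the documents do not support them:

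- A reader might infer that four stained biopsies must cover three visits, an average of 4/3 = 1.33 each, and hence a threefold variance (standard error √3 = 1.73 times larger). No section describes such sharing. The 1/n variance rule also belongs to a mean per biopsy; for a raw total, the harm from unequal tissue is a shift in the expected count.
- A reader might infer that the risk section rests on the figure of 20. Section 21.1 contains no biopsy number.
- A reader might infer that the power statement is undermined. It does not use biopsy number.

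**Conclusion.** The point holds in two parts. As written, the Lab Procedures text and the three visit descriptions contradict each other: 20 against at most 60 biopsies per participant. A figure per procedure is probably meant, but this is inferred from the layout and not stated.

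Independently of how that is resolved, the primary outcome is a raw count from an amount of tissue that the plan does not fix. The possible distortion reaches a factor of 1.96 from biopsy size alone, provided that size is a diameter and in the extreme case only. The documents give no data on biopsy yield or on variation between biopsies, so the likely distortion cannot be estimated.

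This is worth correcting because it concerns the primary endpoint and can still be handled at analysis. It does not invalidate the design. Which biopsy number is clinically appropriate is not judged here.

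**What to change.** - Reconcile the Lab Procedures text with Visits 2, 4 and 5 in section 12.9 to one figure, stated both per procedure and per participant, and give that figure in section 21.1.
- Before analysis, redefine the primary outcome in 12.7 as neurons and glia per imaged submucosal area at each visit, or at least per imaged biopsy, and name the same quantity in 12.10.
- Report, for each participant and visit, the number of biopsies obtained and the number imaged.
- For any tissue not yet allocated, use the same number of stained biopsies at every visit and fill that number before sequencing.

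The first item is wording only. The others cost a little extra image measurement and, where yield is short, some sequencing material. The sample size and the stated power do not change. If collection is already complete, the wording, the denominator and the reporting can still be put in place.

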**12.12 \* Will samples be coded?**

☒ Yes ☐ No

If Yes, Please describe coding scheme consistent with GCP. If samples will not be coded, please provide justification for this proposed departure from GCP practice.

Samples from participants seen at RUH will be coded with the alphanumeric IRB approval followed by

P (denotes participant), and then a consecutive number starting with 001.

For example: YAL-10xx-P-001, YAL-10xx-P-002, YAL-10xx-P-003, etc.

If available, upload the Data and Sample Sharing Management Plan approved by RU IT.

Version	Title	Category	Expiration Date	Document Outcome	View Document
---------	-------	----------	-----------------	------------------	---------------

No Document(s) have been attached to this form.

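### No masking of the cell count to visit is described in an open-label study without a control condition, so a reader's expectation could enter the before/after difference in full

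*Combined protocol and SAP*

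**What the plan says.** - Section 12.7 defines the primary outcome: "Total number of colonic submucosal neurons and glia cells in humans before and after course of antibiotics".
- Lab Procedures (12.9) gives the whole counting method: "We will image the samples with a confocal microscope, and we will count the neurons and glia". It names no reader, masking, second reader, counting rule or automated count, and no other section adds one.
- Section 10.1 ticks open label and 15.2 says that no placebo is used. Section 12.9 opens with "One set of samples will be studied: Colorectal sample tissue and stool from amoxicillin-treated participants".
- Section 12.1 states the expected direction: a marked but temporary loss or alteration of neurons.
- Section 12.12 builds the code from the study number, then "P (denotes participant), and then a consecutive number starting with 001". The examples carry no visit or specimen element: "For example: YAL-10xx-P-001, YAL-10xx-P-002, YAL-10xx-P-003, etc".
- Each participant is biopsied at Visits 2, 4 and 5. For the counted tissue, "four biopsies will be pinned and fixed in 4% paraformaldehyde overnight, followed by washing, permeabilization, and staining of the tissue". The plan does not say when staining or imaging takes place, or whether one participant's visits are processed together. Only the frozen sequencing biopsies are said to be held until several samples have accumulated.
- Section 12.10 compares baseline with follow-up by a paired t-test in 10 participants, at a 5% Type I error.

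**The concern.** A count from confocal images involves judgement about what is a cell and where the field ends. The laboratory expects fewer neurons after antibiotics, and nothing in the plan keeps visit from the person counting. Pairing removes differences between people, but not a difference in how two visits are read. With no concurrent untreated condition, such a difference cannot be told apart from an antibiotic effect.

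The same holds for stain or imaging drift, but only for the part that runs in visit order. Baseline tissue is always collected first, so steady one-way drift would push every pair in the same direction if tissue is processed as it arrives.

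At stake are the nominal 5% error rate and the observed effect size that 12.11 intends to carry into later study designs.

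**Working it through.** **1. The plan's own figure.** Section 12.10 claims more than 80% power for a 1.3 SD change with 10 participants. Inputs are n = 10, df = 9 and two-sided alpha 0.05 (sidedness is not stated, so two-sided is assumed). SD is taken as that of the paired difference. The noncentrality is d × √n = 1.3 × √10 = 4.11, which gives power of 95.4%. The claim is true on this reading. Masking changes neither n nor the nominal power; it protects the 5%.

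**2. How little shift is needed.** The critical t on 9 df is 2.262. An observed mean difference of 2.262 / √10 = 0.72 SD reaches p < 0.05, whatever its source.

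**3. False-positive rate under a visit-linked shift.** Assume no true change and a systematic shift b in units of the SD of the paired difference. Then P(p < 0.05) = P(|T| > 2.262), where T is noncentral t with df 9 and noncentrality b√10.

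| b (SD of difference) | b√10 | False-positive rate |
|---|---|---|
| 0 | 0 | 5.0% |
| 0.1 | 0.32 | 5.9% |
| 0.125 | 0.40 | 6.5% |
| 0.25 | 0.79 | 10.9% |
| 0.5 | 1.58 | 29.3% |

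**4. Sensitivity to the unknown SD.** The documents give no SD for the counts and no reader-agreement or batch figure. Take a 5% shift in the count as an assumption:
- SD of the difference 20% of baseline: 5/20 = 0.25 SD, giving 10.9%.
- SD 40%: 5/40 = 0.125 SD, giving 6.5%.
- SD 50%: 5/50 = 0.1 SD, giving 5.9%.

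The same shift can be material or almost negligible, depending on an SD that nobody has stated.

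**5. Time between visits.** Visit 3 is 14–21 days after Visit 2, and Visit 4 is 5–9 days after antibiotics start. If they start at Visit 3, Visit 2 to Visit 4 is 14 + 5 = 19 to 21 + 9 = 30 days. Visit 5 follows 21–30 days later, so Visit 2 to Visit 5 is 19 + 21 = 40 to 30 + 30 = 60 days.

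**6. How far stain drift follows visit.** Entry is staggered: 17.1 projects 13 weeks to complete accrual and 17.2 ticks 12 months. A single antibody-lot change affects only pairs that straddle it. With uniform accrual (an assumption), that is about 19/91 to 30/91 = 21–33% of pairs over 13 weeks, or 19/365 to 30/365 = 5–8% over 12 months. A 10% lot step would then move the mean difference by about 0.5% (10% × 5%) to 3.3% (10% × 33%) of the count. Batch variation unrelated to visit does not bias the mean; it widens the SD. An added 50% in variance lowers power at 1.3 SD from 95% to 85%. Steady drift and reader expectation are the routes that reach every pair.

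**The case against.** **Silence is not evidence of unmasked reading.** This stands. A reader might infer that the counts are made unmasked, but the documents do not say so. Open label in 10.1 describes the study and not the image reader, and 12.1 refers to established laboratory techniques that are not reproduced here. The supportable statement is that no masking is described.

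**A code without a visit element does not create bias.** This also stands; such a code could even help masking. One might infer that any label added to separate visits must reveal the visit, but a random suffix would not. What 12.12 shows is only that no specimen-level masked ID is specified, although three visits share one participant code.

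**Stain drift is not fully confounded with treatment.** Agreed. Visit-order staining is implied by the workflow and not stated. Staggered entry lets one person's Visit 4 share a run with another's Visit 2. Visit 5 gives a partial check, since recovery would reverse a loss while steady drift would continue. None of this protects against a reader who knows the visit and expects loss followed by recovery.

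**There may be a comparator.** Section 12.9 says participants "will be divided into two groups of 5 and matched in age", and Visit 3 says "Participants will be randomized to receive a 7-day supply of amoxicillin 875mg capsules". No second condition is defined, and randomization is unticked in 31.2 and 35.1. These passages need reconciling, but they supply no control.

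**It is an exploratory pilot.** True, and it limits the weight of any p-value. Section 12.10 nevertheless states a 5% error rate, and a biased effect size would still carry forward.

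**Conclusion.** The point holds as a gap in the description of the primary measurement. No masking to visit and no masked specimen ID are set out for a reader-dependent count, in a study whose only defined contrast is visit against visit. Reader expectation linked to visit would enter the paired difference in full; staining or imaging drift would do so only in the part that follows visit order.

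The size is unknown. The rates of 5.9%, 10.9% and 29.3% at 0.1, 0.25 and 0.5 SD are illustrations. They rest on n = 10, a two-sided 5% paired t-test, no true change and an assumed constant shift. They are not estimates of the bias in this study, and the documents do not show that any bias has occurred. The change is worth making because the safeguard costs very little.

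**What to change.** 1. **Section 12.12:** give each image a random ID unrelated to participant or visit. Keep the key away from the person counting.
2. **Section 12.9:** state that all images are counted masked and in random order, and that the key is released only after the counts are locked.
3. **If counting is already done:** re-count the stored images masked. The study closed to enrollment on May 24, 2024 and projects no visits in the next year, so this may be the practical route.
4. **Staining and imaging:** record the run for each specimen and report whether runs are balanced across visits. Where tissue is still unstained, spread visits across runs. Process one participant's visits together only if the difference in storage time is acceptable and reported: holding all tissue to the last visit would store Visit 2 tissue about 40–60 days longer than Visit 5 tissue, which ties storage time to visit.

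**Cost:** a renaming script and some re-count time. No extra reader, participant or procedure is needed. Masked re-counting removes reader expectation but cannot undo stain differences already in the tissue; those can only be reported.
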